8.2.3. Serious Adverse Events

A serious adverse event is any untoward medical occurrence at any dose that:

- Results in death;
- Is life-threatening (immediate risk of death);
- Requires inpatient hospitalization or prolongation of existing hospitalization;
- Results in persistent or significant disability/incapacity (substantial disruption of the ability to conduct normal life functions);
- Results in congenital anomaly/birth defect.

Or that is considered to be:

- An important medical event.

Medical and scientific judgment is exercised in determining whether an event is an important medical event. An important medical event may not be immediately life-threatening and/or result in death or hospitalization. However, if it is determined that the event may jeopardize the subject or may require intervention to prevent one of the other AE outcomes, the important medical event should be reported as serious.

Examples of such events are intensive treatment in an emergency room or at home for allergic bronchospasm; blood dyscrasias or convulsions that do not result in hospitalization; or development of drug dependency or drug abuse.

Progression of the malignancy under study (including signs and symptoms of progression) should not be reported as an SAE unless the outcome is fatal within the active collection period. Hospitalization due to signs and symptoms of disease progression should not be reported as an SAE. If the malignancy has a fatal outcome during the study or within the active collection period, then the event leading to death must be recorded as an AE on the CRF, and as an SAE with Common Terminology Criteria for Adverse Events (CTCAE) Grade 5 (see the [Severity Assessment](#) section).

8.2.4. Hospitalization

Hospitalization is defined as any initial admission (even less than 24 hours) in a hospital or equivalent healthcare facility, or any prolongation of an existing admission. Admission also includes transfer within the hospital to an acute/intensive care unit (eg, from the psychiatric wing to a medical floor, medical floor to a coronary care unit, or neurological floor to a tuberculosis unit). An emergency room visit does not necessarily constitute a hospitalization; however, the event leading to the emergency room visit is assessed for medical importance.

Hospitalization does not include the following:

- Rehabilitation facilities;
- Hospice facilities;
- Respite care (eg, caregiver relief);
- Skilled nursing facilities;
- Nursing homes;
- Same-day surgeries (as outpatient/same-day/ambulatory procedures).

Hospitalization or prolongation of hospitalization in the absence of a precipitating clinical AE is not in itself an SAE. Examples include:

- Admission for treatment of a preexisting condition not associated with the development of a new AE or with a worsening of the preexisting condition (eg, for workup of a persistent pretreatment laboratory abnormality);
- Social admission (eg, subject has no place to sleep);
- Administrative admission (eg, for yearly physical examination);
- Protocol-specified admission during a study (eg, for a procedure required by the study protocol);
- Optional admission not associated with a precipitating clinical AE (eg, for elective cosmetic surgery);
- Hospitalization for observation without a medical AE;
- Preplanned treatments or surgical procedures. These should be noted in the baseline documentation for the entire protocol and/or for the individual subject;
- Admission exclusively for the administration of blood products.

Diagnostic and therapeutic noninvasive and invasive procedures, such as surgery, should not be reported as SAEs. However, the medical condition for which the procedure was performed should be reported if it meets the definition of an SAE. For example, an acute appendicitis that begins during the reporting period should be reported if the SAE requirements are met, and the resulting appendectomy should be recorded as treatment of the AE.

8.3. Severity Assessment

For oncology studies, investigators report AEs using concise medical terminology (verbatim) as well as collect on the *CRF* the appropriate Common Terminology Criteria for Adverse Events (CTCAE) (Version 4.03, Publish Date: 14 June 2010, <http://ctep.cancer.gov/reporting/ctc.html>) listed in the Cancer Therapy Evaluation Program.

The investigator will use the following definitions of severity in accordance with the current CTCAE version to describe the maximum intensity of the adverse event.

GRADE	Clinical Description of Severity
0	No change from normal or reference range (This grade is not included in the Version 4.03 CTCAE document but may be used in certain circumstances.)
1	MILD adverse event
2	MODERATE adverse event
3	SEVERE adverse event
4	LIFE-THREATENING consequences; urgent intervention indicated
5	DEATH RELATED TO adverse event

8.4. Special Situations

8.4.1. Protocol-Specified Serious Adverse Events

There are no protocol-specified SAEs in this study. All SAEs will be reported to Pfizer Safety by the investigator as described in previous sections, and will be handled as SAEs in the safety database.

8.4.2. Potential Cases of Drug-Induced Liver Injury

Humans exposed to a drug who show no sign of liver injury (as determined by elevations in transaminases) are termed “tolerators,” while those who show transient liver injury, but adapt are termed “adaptors.” In some subjects, transaminase elevations are a harbinger of a more serious potential outcome. These subjects fail to adapt and therefore are “susceptible” to progressive and serious liver injury, commonly referred to as drug-induced liver injury (DILI). Subjects who experience a transaminase elevation above 3 times the upper limit of normal (\times ULN) should be monitored more frequently to determine if they are an “adaptor” or are “susceptible.”

In the majority of DILI cases, elevations in aspartate aminotransferase (AST) and/or alanine aminotransferase (ALT) precede total bilirubin (TBili) elevations ($>2 \times$ ULN) by several days or weeks. The increase in TBili typically occurs while AST/ALT is/are still elevated above $3 \times$ ULN (ie, AST/ALT and TBili values will be elevated within the same lab sample). In rare instances, by the time TBili elevations are detected, AST/ALT values might have decreased. This occurrence is still regarded as a potential DILI. Therefore, abnormal elevations in either AST OR ALT in addition to TBili that meet the criteria outlined below are considered potential DILI (assessed per Hy’s law criteria) cases and should always be considered important medical events, even before all other possible causes of liver injury have been excluded.

The threshold of laboratory abnormalities for a potential DILI case depends on the subject's individual baseline values and underlying conditions. Subjects who present with the following laboratory abnormalities should be evaluated further as potential DILI (Hy's law) cases to definitively determine the etiology of the abnormal laboratory values:

- Subjects with AST/ALT and TBili baseline values within the normal range who subsequently present with AST OR ALT values $>3 \times \text{ULN}$ AND a TBili value $>2 \times \text{ULN}$ with no evidence of hemolysis and an alkaline phosphatase value $<2 \times \text{ULN}$ or not available;
- For subjects with baseline AST **OR** ALT **OR** TBili values above the ULN, the following threshold values are used in the definition mentioned above, as needed, depending on which values are above the ULN at baseline:
 - Preexisting AST or ALT baseline values above the normal range: AST or ALT values >2 times the baseline values AND $>3 \times \text{ULN}$; or $>8 \times \text{ULN}$ (whichever is smaller).
 - Preexisting values of TBili above the normal range: TBili level increased from baseline value by an amount of at least $1 \times \text{ULN}$ **or** if the value reaches $>3 \times \text{ULN}$ (whichever is smaller).

Rises in AST/ALT and TBili separated by more than a few weeks should be assessed individually based on clinical judgment; any case where uncertainty remains as to whether it represents a potential Hy's law case should be reviewed with the sponsor.

The subject should return to the investigator site and be evaluated as soon as possible, preferably within 48 hours from awareness of the abnormal results. This evaluation should include laboratory tests, detailed history, and physical assessment.

In addition to repeating measurements of AST and ALT and TBili, laboratory tests should include albumin, creatine kinase (CK), direct and indirect bilirubin, gamma-glutamyl transferase (GGT), prothrombin time (PT)/international normalized ratio (INR), total bile acids, alkaline phosphatase and acetaminophen drug and/or protein adduct levels. Consideration should also be given to drawing a separate tube of clotted blood and an anticoagulated tube of blood for further testing, as needed, for further contemporaneous analyses at the time of the recognized initial abnormalities to determine etiology. A detailed history, including relevant information, such as review of ethanol, acetaminophen (either by itself or as a coformulated product in prescription or over-the-counter medications), recreational drug, supplement (herbal) use and consumption, family history, sexual history, travel history, history of contact with a jaundiced person, surgery, blood transfusion, history of liver or allergic disease, and potential occupational exposure to chemicals, should be collected. Further testing for acute hepatitis A, B, C, D, and E infection and liver imaging (eg, biliary tract) may be warranted.

All cases demonstrated on repeat testing as meeting the laboratory criteria of AST/ALT and TBili elevation defined above should be considered potential DILI (Hy's law) cases if no other reason for the LFT abnormalities has yet been found. **Such potential DILI (Hy's law) cases are to be reported as SAEs, irrespective of availability of all the results of the investigations performed to determine etiology of the LFT abnormalities.**

A potential DILI (Hy's law) case becomes a confirmed case only after all results of reasonable investigations have been received and have excluded an alternative etiology.

8.4.3. Exposure to the Investigational Product During Pregnancy or Breastfeeding, and Occupational Exposure

Exposure to the investigational product under study during pregnancy or breastfeeding and occupational exposure are reportable to Pfizer Safety within 24 hours of investigator awareness.

8.4.3.1. Exposure During Pregnancy

For both unapproved/unlicensed products and for marketed products, an exposure during pregnancy (EDP) occurs if:

- A female becomes, or is found to be, pregnant either while receiving or having been exposed (eg, because of treatment or environmental exposure) to the investigational product; or the female becomes or is found to be pregnant after discontinuing and/or being exposed to the investigational product;
- An example of environmental exposure would be a case involving direct contact with a Pfizer product in a pregnant woman (eg, a nurse reports that she is pregnant and has been exposed to chemotherapeutic products).
- A male has been exposed (eg, because of treatment or environmental exposure) to the investigational product prior to or around the time of conception and/or is exposed during his partner's pregnancy.

If a subject or subject's partner becomes or is found to be pregnant during the subject's treatment with the investigational product, the investigator must report this information to Pfizer Safety on the CT SAE Report Form and an EDP supplemental form, regardless of whether an SAE has occurred. In addition, the investigator must submit information regarding environmental exposure to a Pfizer product in a pregnant woman (eg, a subject reports that she is pregnant and has been exposed to a cytotoxic product by inhalation or spillage) to Pfizer Safety using the EDP supplemental form. This must be done irrespective of whether an AE has occurred and within 24 hours of awareness of the exposure. The information submitted should include the anticipated date of delivery (see below for information related to termination of pregnancy).

Follow-up is conducted to obtain general information on the pregnancy and its outcome for all EDP reports with an unknown outcome. The investigator will follow the pregnancy until completion (or until pregnancy termination) and notify Pfizer Safety of the outcome as a

follow-up to the initial EDP supplemental form. In the case of a live birth, the structural integrity of the neonate can be assessed at the time of birth. In the event of a termination, the reason(s) for termination should be specified and, if clinically possible, the structural integrity of the terminated fetus should be assessed by gross visual inspection (unless pre-procedure test findings are conclusive for a congenital anomaly and the findings are reported).

If the outcome of the pregnancy meets the criteria for an SAE (ie, ectopic pregnancy, spontaneous abortion, intrauterine fetal demise, neonatal death, or congenital anomaly [in a live-born baby, a terminated fetus, an intrauterine fetal demise, or a neonatal death]), the investigator should follow the procedures for reporting SAEs.

Additional information about pregnancy outcomes that are reported to Pfizer Safety as SAEs follows:

- Spontaneous abortion includes miscarriage and missed abortion;
- Neonatal deaths that occur within 1 month of birth should be reported, without regard to causality, as SAEs. In addition, infant deaths after 1 month should be reported as SAEs when the investigator assesses the infant death as related or possibly related to exposure to the investigational product.

Additional information regarding the EDP may be requested by the sponsor. Further follow-up of birth outcomes will be handled on a case-by-case basis (eg, follow-up on preterm infants to identify developmental delays). In the case of paternal exposure, the investigator will provide the subject with the Pregnant Partner Release of Information Form to deliver to his partner. The investigator must document in the source documents that the subject was given the Pregnant Partner Release of Information Form to provide to his partner.

8.4.3.2. Exposure During Breastfeeding

Scenarios of exposure during breastfeeding must be reported, irrespective of the presence of an associated SAE, to Pfizer Safety within 24 hours of the investigator's awareness, using the CT SAE Report Form. An exposure during breastfeeding report is not created when a Pfizer drug specifically approved for use in breastfeeding women (eg, vitamins) is administered in accord with authorized use. However, if the infant experiences an SAE associated with such a drug's administration, the SAE is reported together with the exposure during breastfeeding.

8.4.3.3. Occupational Exposure

An occupational exposure occurs when, during the performance of job duties, a person (whether a healthcare professional or otherwise) gets in unplanned direct contact with the product, which may or may not lead to the occurrence of an AE.

An occupational exposure is reported to Pfizer Safety within 24 hours of the investigator's awareness, using the CT SAE Report Form, regardless of whether there is an associated SAE. Since the information does not pertain to a subject enrolled in the study, the information is not recorded on a CRF; however, a copy of the completed CT SAE Report Form is maintained in the investigator site file.

8.4.4. Medication Errors and Lack of Efficacy

Other exposures to the investigational product under study may occur in clinical trial settings, such as medication errors and lack of efficacy.

Safety Event	Recorded on the CRF	Reported on the CT SAE Report Form to Pfizer Safety Within 24 Hours of Awareness
Medication errors and lack of efficacy*	All (regardless of whether associated with an AE)	Only if associated with an SAE

*For lack of efficacy (particularly for studies conducted with vaccines, contraceptives, and products used in the treatment of life-threatening diseases or conditions [eg, anti-infectives]), see the Lack of Efficacy section below.

8.4.4.1. Medication Errors

Medication errors may result from the administration or consumption of the investigational product by the wrong subject, or at the wrong time, or at the wrong dosage strength, or inadvertent exposure.

Medication errors include:

- Medication errors involving subject exposure to the investigational product;
- Potential medication errors or uses outside of what is foreseen in the protocol that do or do not involve the participating subject.

Such medication errors occurring to a study participant are to be captured on the medication error page of the CRF, which is a specific version of the AE page.

In the event of a medication dosing error, the sponsor should be notified immediately.

Whether or not the medication error is accompanied by an AE, as determined by the investigator, the medication error is recorded on the medication error page of the CRF and, if applicable, any associated AE(s), serious and non-serious, are recorded on an AE page of the CRF.

Medication errors should be reported to Pfizer Safety within 24 hours on a CT SAE Report Form **only when associated with an SAE**.

8.4.4.2. Lack of Efficacy

Lack of efficacy is reportable to Pfizer Safety only if associated with an SAE.

9. DATA ANALYSIS/STATISTICAL METHODS

Detailed methodology for summary and statistical analyses of the data collected in this study will be documented in a Statistical Analysis Plan, which will be maintained by the sponsor. This document may modify the plans outlined in the protocol; however, any major modifications of the endpoint definition and/or its analysis will also be reflected in the clinical study report.

9.1. Sample Size Determination

This study does not include any formal sample size determination. All bosutinib patients from the two parent studies B1871006 and B871008 who are still on-treatment at the initiation of this study, or known to be alive as of their last LTFU visit, or who have completed the parent study will be offered enrollment in this extension study.

9.2. Analysis of Efficacy

Data from the two parent studies will be combined with the data from this study for the analysis of efficacy. All bosutinib patients randomized in parent Study B1871008 or dosed in parent Study B1871006 will be included in the efficacy analyses. Analyses will be presented by disease stage (ie, CP, AP, BP) and by line of therapy.

Descriptive summaries and confidence intervals (if applicable) will be provided; no inferential analyses are planned for this study.

The time-to-event endpoints of overall survival, time to transformation, progression-free survival, and duration of response will be summarized via the Kaplan-Meier method or cumulative incidence,² whichever is more appropriate, depending on the presence of competing risk.

9.3. Overall Survival

Overall survival (OS) or survival time is defined as the interval from the date of randomization (first line patients enrolled from B1871008) or first dosing (second or later line patients enrolled from B1871006) in the parent study to the date of death due to any cause. Patients not known to have died are censored at the last known alive date. OS will be calculated for all patients enrolled in the parent study B1871008 and dosed in the parent study B1871006.

9.4. Time to Transformation to AP/BP

Time to transformation is defined as the time from the date of first dose in the parent study to the first date of confirmed transformation to AP or BP. For patients without transformation, censorship is at the last evaluation date.

Time to transformation will be calculated only for patients in 2nd or plus line setting while on treatment.

9.5. Progression-Free Survival

Progression-free survival (PFS) is the interval from the date of first dose of bosutinib in the parent study until the earlier date of progression or death from any cause. Patients without events are censored at the last evaluation date.

PFS will be calculated only for patients in 2nd or above line setting.

9.6. Duration of Response

Duration of response (MCyR, CHR, OHR) is measured from the date of the earliest demonstration of a response, until the earliest date of confirmed loss of that response. For patients without loss of response, censorship is at the last evaluation date. Duration of response will be calculated only for patients in 2nd or plus line setting who respond to treatment.

9.7. Safety Analysis

Treatment-emergent AE (defined as any event increasing in severity from parent study baseline, or any new event starting during bosutinib therapy or within 30 days of the last bosutinib dose) incidence rates will be described both with and without regard to causality. The frequency of occurrence of overall toxicity, categorized by toxicity grades, will be described. Listings of laboratory test results collected at baseline and during the study will be generated and descriptive statistics summarizing changes in laboratory tests over time will be presented.

The incidence of diarrhea from the 2 parent studies and the incidence of diarrhea from extension study will be tabulated in order to compare the clinical and commercial formulations of bosutinib.

The pharmacokinetic analysis (collected for all patients except those from sites in China) will compare the C_{trough} of bosutinib in this study to C_{trough} of previous studies.

All patients dosed in the parent Studies B1871006 and B1871008 will be included in the safety analyses. Data from the two parent studies will be combined with the data from this study for the analysis of safety.

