6.3. Treatment Completion Visit

The End of Treatment (EOT) visit should be performed for all patients once they have permanently discontinued bosutinib as described in [Section 5.3](#). The visit should occur within 28 days after the last dose of bosutinib. The following procedures are required:

- Complete physical examination including vital signs, ECOG performance status and extramedullary disease assessment;
- Electrocardiogram (ECG);
- Chest X-ray;
- Mutation analysis of the BCR-ABL1 transcript will be performed using a peripheral blood sample collected at the end-of-treatment visit in order to identify mutations acquired upon treatment with bosutinib. Mutations will be identified by direct sequencing of the BCR-ABL transcript performed at a Central Laboratory as arranged by the Sponsor. Peripheral blood for all eligible patients (except from patients enrolled at sites in China) will be collected and shipped frozen to a central vendor for analysis. Specific instructions for handling and shipment of these samples can be found in Study Reference Manual;
- Cytogenetic or residual molecular response testing. Molecular response monitoring using reverse transcriptase polymerase chain reaction (RT-PCR) measurement of BCR-ABL fusion transcript levels in peripheral blood may be performed in lieu of monitoring via cytogenetics, once molecular response is achieved, and according to standard of care and current treatment guidelines at investigative site;

- Hematology panel with complete blood counts (CBC) (see [Section 6.1](#) for details);
- Chemistry panel(see [Section 6.1](#) for details);
- Liver Function Tests (LFTs) (see [Section 6.1](#) for details);
- Coagulation tests (see [Section 6.1](#) for details);
- Dipstick urinalysis (microscopic if abnormal);
- Serum pregnancy test (for women of childbearing potential);
- Contraceptive check;
- Dosing compliance check;
- Review of adverse events and concomitant medications.

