6.4. Long-Term Follow-up Visit

Patients who discontinue treatment with bosutinib prior to the end of the study will enter into the Long-Term Follow-Up period. Patients will be followed for the duration of study in order to assess the survival status of the patient. Details of any subsequent therapy with TKIs or other anti-cancer therapy and response following bosutinib discontinuation will be collected on LTFU patients if available.

Follow-up will be conducted every 3 months from the last dose of bosutinib. Information will be collected via clinical visit or telephone contact

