7.2. Safety Assessments

Refer to the [Schedule Of Activities](#) for time points.

Adverse events will be graded according to the National Cancer Institute Common Terminology Criteria for Adverse Events (NCI CTCAE), version 3.0. Patients are to be followed for adverse events for 28 days after last dose of bosutinib, regardless of causality. Furthermore, all treatment-related adverse events will be followed until Grade ≤ 1 , return to baseline, or in the case of impairment, until the condition stabilizes.

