8.1.4. Time Period for Collecting AE/SAE Information

The time period for actively eliciting and collecting AEs and SAEs (“active collection period”) for each subject begins from the time the subject provides informed consent, which is obtained before the subject’s participation in the study (ie, before undergoing any study-related procedure and/or receiving investigational product), through and including a minimum of [28 calendar days; except as indicated below] after the last administration of the investigational product.

For subjects who are screen failures, the active collection period ends when screen failure status is determined.

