8.1.4.2. Recording Non-serious AEs and SAEs on the CRF

During the active collection period, both non-serious AEs and SAEs are recorded on the CRF.

Follow-up by the investigator may be required until the event or its sequelae resolve or stabilize at a level acceptable to the investigator, and Pfizer concurs with that assessment.

If a patient begins a new anticancer therapy, the recording period for non-serious AEs ends at the time the new treatment is started; however, SAEs must continue to be recorded on the CRF during the above-indicated active collection period.

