6. ENDPOINTS AND COVARIATES

There is no formal hypothesis testing therefore endpoints are not designated as primary or secondary.

In general, the baseline value will be defined as the last non-missing value prior to first dose from B1871008 and B1871006, unless specifically stated otherwise. Assessments performed on Week 1 day 1 will be assumed to be pre-dose per the schedule of activities in the Protocol.

An on-treatment efficacy evaluation is defined as any evaluation done during bosutinib therapy or within 30 days of last dose for B1871008 patients and up to date of treatment discontinuation for B1871006 patients. An on-treatment safety evaluation is defined as any evaluation done during bosutinib therapy or within 30 days of last dose.

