6.2. Safety Endpoints

Treatment-emergent adverse events (TEAE) were defined as any event increasing in severity from baseline or any new event starting during bosutinib therapy or within 30 days of the last dose of study drug.

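### New adverse events count as treatment-emergent to day 30 after the last dose, but collection is required only for a minimum of 28 days and Schedule B has no AE contact after the End of Treatment visit

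*Protocol*

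**What the plan says.** **Analysis window.** Protocol 9.7 counts "any new event starting during bosutinib therapy or within 30 days of the last bosutinib dose". SAP 6.2 matches it: "any new event starting during bosutinib therapy or within 30 days of the last dose of study drug". The SAP also uses 30 days elsewhere. Section 6 states: "An on-treatment safety evaluation is defined as any evaluation done during bosutinib therapy or within 30 days of last dose". SAP 6.2.4 uses 30 days for concomitant medications and SAP 6.2.5 for deaths.

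**Collection window.** Protocol 7.2 states: "Patients are to be followed for adverse events for 28 days after last dose of bosutinib, regardless of causality". Protocol 8.1.4 runs active collection "through and including a minimum of [28 calendar days; except as indicated below] after the last administration of the investigational product".

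**Scheduled contacts.** Protocol 6.3 says of the End of Treatment visit: "The visit should occur within 28 days after the last dose of bosutinib". In Table 1, Schedule B, the AE row is marked at the initial visit, Month 3, the 6-monthly visits, the phone calls and End of Treatment. It has no mark under long-term follow-up. Protocol 6.4 gives the purpose of that phase: "Patients will be followed for the duration of study in order to assess the survival status of the patient". It adds details of later therapy, and contacts are every 3 months from the last dose.

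**New therapy.** Under Protocol 8.1.4.2, once a new anticancer therapy begins, "the recording period for non-serious AEs ends at the time the new treatment is started". SAEs are still recorded to the end of the active collection period.

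**The concern.** A treatment-emergent window means what it says only if events are sought throughout it. Here three rules do not line up.

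- The window is 30 days and the required collection floor is 28.
- The duty to elicit AEs to day 28 has no scheduled contact attached to it. A site that holds the End of Treatment visit on day 2 is within the visit rule, and its next planned contact is about day 84 (3 months of 28 days). That contact is not set up to ask about AEs.
- After a switch of therapy within the window, an SAE is recorded and meets the TEAE definition, while a non-serious event is not recorded. The definition in Protocol 9.7 and SAP 6.2 does not mention this.

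What is at stake is even capture of events just after bosutinib is stopped, in a study whose stated endpoints begin with long-term safety. It could depend on when each site books one visit and on how soon a patient changes therapy.

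**Working it through.** The plan states no figure for this point, so there is nothing to reproduce. The check is arithmetic on the windows.

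**Inputs**
- TEAE window W = 30 days (Protocol 9.7, SAP 6.2).
- Required collection C = 28 days as a minimum (Protocol 7.2, 8.1.4).
- End of Treatment visit on day v, with v from 0 to 28 (Protocol 6.3, Schedule B).
- Median duration of therapy 11 months (the larger Phase 1/2 study) and 16.6 months (Phase 3), from the pooled safety data in Protocol 1.2.2, cutoff 15 November 2010.
- 30.4 days per month, the SAP 6.2.1 conversion.

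**1. Days in the window without required collection**

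W − C = 30 − 28 = 2 days, and 2/30 = 7%.

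**2. Days after the last scheduled AE contact (W − v)**

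| Visit day v | Days to day 30 | Share of 30 | Days to day 28 |
|---|---|---|---|
| 0 | 30 | 100% | 28 |
| 7 | 23 | 77% | 21 |
| 14 | 16 | 53% | 14 |
| 21 | 9 | 30% | 7 |
| 28 | 2 | 7% | 0 |

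The documents give no distribution of visit days. If visits were spread evenly over days 0 to 28 (assumption), the mean would be 30 − 14 = 16 days. These are days without a scheduled contact. They are neither days without a duty to collect nor a share of events.

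**3. Switch to a new anticancer therapy on day s**

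Non-serious events go unrecorded for about 30 − s days of the window: 29 days for s = 1, 23 for s = 7 and 16 for s = 14. For SAEs, the days without required collection stay at 2.

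**4. Share of total time at risk (therapy plus 30 days)**
- 11 months: 11 × 30.4 + 30 = 364.4 days. The 2 days are 2/364.4 = 0.5%, and the full 30 days are 30/364.4 = 8.2%.
- 16.6 months: 16.6 × 30.4 + 30 = 534.6 days. The 2 days are 2/534.6 = 0.4%, and the full 30 days are 30/534.6 = 5.6%.

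**5. Two possible remedies**
- Cutting the definition to 28 days removes the 2-day mismatch. It still leaves up to 28 of 28 days after the last scheduled AE contact when v = 0.
- An AE question covering the period through day 30 leaves 30 − 30 = 0 days uncovered, apart from non-serious events after a switch.

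**The case against.** The strongest reply is that the duty to collect is already written and does not end at the visit. Protocol 7.2 requires AE follow-up for 28 days, and 8.1.4 requires active elicitation over the same period. A site that visits on day 2 and asks nothing more satisfies 6.3 but breaches both. Protocol 8.1.4 sets a floor, so events on days 29 and 30 may be recorded. Under 8.1.4.1 and the long-term follow-up footnotes to Table 1, SAEs after the active period are reported if the investigator learns of them. Table 1 is described as an overview, and unplanned visits needed for patient well-being are allowed.

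This stands. A reader might infer that AEs are not collected after day 28, or that half or all of the post-dose window is lost when the visit is early. The documents support neither. What remains is that no contact is named for discharging the duty, and that reporting after day 28 is passive and covers SAEs only.

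On new therapy, stopping non-serious recording is an explicit rule. A reader might infer that SAEs due to the next drug are passed off as bosutinib effects. That goes too far: 8.1.5 requires a causality assessment for every AE, Protocol 9.7 describes TEAEs both with and without regard to causality, and SAP 8.2.2.7 tabulates related TEAEs separately. The unequal capture in the all-causality tables remains. It is also tempting to say that patients who stop for toxicity or progression have the most post-dose events and switch quickly. The documents show neither, so both are assumptions.

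Finally, shortening the TEAE window to 28 days looks like the natural remedy. It would put TEAEs out of step with the 30-day windows in SAP 6 and 6.2.4. It could also drop parent-study events on days 29 and 30 from the pooled tables, since the parent studies' collection windows are not given.

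**Conclusion.** The mismatch is real and no section reconciles it. Required collection falls 2 days short of the 30-day window. The time after the last scheduled AE contact is 2 to 30 days, depending on when the End of Treatment visit is held. After a switch, serious and non-serious TEAEs are captured unequally.

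The effect on overall TEAE rates is likely small. At the quoted medians the 2 days are about 0.5% or less of time at risk, those medians come from an early cutoff, and the tables pool all patients dosed in the parent studies. The study has no hypotheses or decision rules for this to affect. Deaths within 30 days are largely protected by survival follow-up.

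The scheduling point rests on Protocol 6.3 and Schedule B, because the columns of Schedule A could not be aligned reliably in the text available. It concerns patients who stop bosutinib in the extension. The change is worth making because it is cheap and improves capture just after stopping; the study's validity does not depend on it.

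**What to change.** 1. **Protocol Table 1 and 6.4.** Where the End of Treatment visit falls before the end of the window, have sites ask about AEs and SAEs from that visit through day 30. This can be a short phone call at the end of the window or a question at the first follow-up contact already scheduled. Since the visit is due by day 28, this applies in practice to every patient who stops bosutinib in the extension. State the same period in 7.2 and 8.1.4. Non-serious events would still be asked about only up to the start of any new anticancer therapy, as 8.1.4.2 provides.

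2. **SAP 6.2 and 8.2.2.7.** Flag TEAEs and SAEs that start after a new anticancer therapy, using the subsequent-therapy dates where available. State that non-serious events are not recorded after that point.

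This matches collection to the existing definition. The 30-day windows in SAP 6, 6.2.4 and 6.2.5 and the pooled parent-study data stay as they are, so the TEAE window need not be shortened.

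**Cost.** One call or one added question per stopping patient, a protocol wording change and a few lines in the SAP. If sites use the 3-month contact, recall will be weaker than with a call at the end of the window.
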